After eligibility is verified during phone screening by team member, the consent will be reviewed verbally, questions about the study will be answered. They will be asked if they verbally consent to the study, with the understanding that the Consent Form will be reviewed and signed prior to the first timepoint (T1) data collection. If they agree to participate, the research team member will then confirm and update any contact information into CWRU Box Screening and Enrollment Log and REDCap form; this includes the individual's full name, mailing address, phone number(s), email address, best time of day to call, and confirming if the study team can leave voice mail messages, text to schedule / confirm study visits and intervention check-ins, and/or send mail to their mailing address if we are having trouble contacting them by phone or email. The study enrollment/first data collection appointment will be made at this time.

If the screenee is not eligible/ declines verbal consent:

If the individual does not meet the study criteria, they are asked if they would like to have their contact information kept on file in the event that the screening criteria are modified (e.g. study radius) and would like to be contacted to re-assess eligibility. If they say yes, the staff member will proceed to collect contact information in CWRU BOX and REDCap form (confirm full name, mailing address, phone number(s), email address).

Screening data (questions asked to determine eligibility) is kept in the REDCap form in which it was entered in for tracking and reporting purposes.

5. Describe the feasibility of recruiting the required number of suitable research participants within the agreed recruitment period. For example, how many potential research participants do you have access to?

Based on previous research by the PI, we conservatively estimate that 20%–45% 58% of caregivers may not meet eligibility criteria. Thus, we will screen ~375–550 600 individuals potential participants to obtain the desired sample size of 300 350.

Setting

Directions: Make sure to describe: 1) sites and locations where your research team will conduct the research; 2) where your research team will identify and recruit potential research participants; and 3) include the physical location where research procedures will be performed.

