There is potential benefit to research participants.

Describe the potential benefits that individual research participants may experience from taking part in the research. Include the probability, magnitude, and duration of the potential benefits.

There is no direct benefit to research participants.

If no direct benefit, state the potential benefit to society or others. *Do not list compensation.*

Withdrawal of Research Participants

Directions: Describe the anticipated circumstances under which research participants will be withdrawn from the research without their consent. Also include the procedures that will be followed when a research participant withdraws or are withdrawn from the research, including partial withdrawal from procedures with continued data collection.

N/A

Participants have the option of withdrawing from the study at any time and can request that no further information be shared about them from that point on. If a study participant withdraws consent to participate in the study, a research team member will notify the project manager to complete end of study documentation.

The project manager will review cases regularly with research staff to determine which study participants should be withdrawn from the study. Research participants will be withdrawn from the research without their consent if they are non-responsive to phone calls, emails, texts, or letters and considered lost to follow up.

Data that were collected prior to a study participant's withdrawal will be de-identified and still be used in the data analysis for the study. After withdrawal, no further data will be collected for that participant.

Alternatives to Participation

Directions: List other options to participation. If subjects will be compensated with extra course credit, the course instructor offering extra course credit must provide alternatives to earn extra course credit. The alternative assignment must require equal or less time and effort for the same amount of earned extra credit that you can earn through participation in research. If there are other available clinical treatments, what would be included if a subject continued on standard of care therapy. If there is a viable alternative you must list it in the consent.

The alternative is for research subjects not to participate.

Costs to Research Participants

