There are no costs to research participants or their insurance companies (there are no clinical visits or billable procedures.) – *You may delete the rest of the section.*

1. Describe what costs research participants will be responsible for as a result of their participation in the research, including but not limited to: clinical services required by the protocol deemed billable to insurance, transportation to study visits, parking, costs of drugs, cost of therapy, lost broken or stolen devices, etc.
2. Explain who will be responsible for payment of provided services in the event of insurance denials.
3. List what procedures, drugs, devices, supplies will be paid by the study sponsor or covered by other funding. List the other funding source.

Research Participant Compensation

There is no compensation for research participants – *please leave rest of this section blank*
 There is compensation for research participants.

Describe the schedule, payment method, and payment total of any incentives or compensation that research participants will receive for participation in the research (e.g., gift cards or cash with amount, t-shirts, devices, bags, swag, etc.)

Gift card incentives will be increased over time: \$20 at T1, \$25 at T2, and \$30 at T3. Carers will also receive a \$20 gift card for the face-to-face intervention session and \$5 gift cards for each week (up to 4 weeks/ \$20) of completion of the workbook, distributed after the 28-day intervention time frame. Thus, each subject may receive up to \$115 in gift card compensation for completion of all study activities.

There will be reimbursement for research participants.
Describe the schedule, payment method, and payment total of any reimbursement that research participants will receive for participation in the research (e.g., gift cards or cash with amount, etc.)

If someone takes a bus or drives to CWRU or other community location to meet a research team member for T1, T2, T3, or an intervention meeting, we will reimburse that individual a 2-trip bus pass or parking voucher as appropriate.

Compensation for Research Related Injury

Describe who will pay for the costs of medical treatment and/or compensation in the event of a research related injury:

- Funding agency is providing some/all payment for injury
- Funding agency is providing no payment for injury
- N/A

Provisions to Monitor the Data to Ensure the Safety of Research Participants

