c) Conformance with informed consent requirements – Random internal audits will be conducted twice per year to verify that informed consent requirements are being met. For example, the SMC will review 10% of the consent forms for signatures and dates, make sure all consent forms are accounted for and stored in locked files and that the correct form is being used. Data collectors will be asked to describe the consent process quarterly to re-assess their knowledge of this process quarterly and review / retraining will be done as needed.

d) Verification of source documents – This study does not involve printed or written documents; data will be collected through electronic data capture using REDcap software and then downloaded directly into SPSSPC files. Heart rate variability data will be downloaded from the assessment device and transcribed into the SPSSPC files. These sources will not include any data that would be personally identifiable.

The SMC will review 1) all causes of mortality (e.g., carer death); 2) issues with participation (e.g., numbers and reasons for withdrawing from the study or refusing interventions, etc.) as well as recruitment refusal (percent and reasons) and subject attrition (percent and reasons); 3) missing data (including whether there are systematic patterns or whether data are missing at random); and 4) errors in data entry (which are expected to be minimal given the use of software for data collection with direct download into SPSS). In addition, differential attrition from the intervention groups (including the control and usual care groups, and the groups assigned to intervention based on need or personal preferences) will be monitored.

If concerns or problems are identified by the SMC, they will be reported to the IRB and NINR/NIH via email by [name] and [name], respectively, within 3 business days after they are identified. If there are recommendations made by the SMC, the action plan for response or notice of any actions taken by the IRB regarding the research and any responses to those actions will be provided to NINR Officials within 2 weeks.

e) Investigator compliance – Compliance of the investigators and all research team members who will have access to the data will be monitored annually. All research team members will be CREC certified; the CWRU intranet hosts a website where verification of compliance with continuing education for all investigators and team members can be evaluated.

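### Carers judged lost to follow-up are withdrawn by staff and data collection then ends, so any later T2 or T3 outcome is given up although they never withdrew consent

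*Combined protocol and SAP*

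**What the plan says.** The rule is in the protocol section Withdrawal of Research Participants, in four parts.

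- Who decides: "The project manager will review cases regularly with research staff to determine which study participants should be withdrawn from the study".
- Trigger: "Research participants will be withdrawn from the research without their consent if they are non-responsive to phone calls, emails, texts, or letters". The sentence does not stop there; in full, it applies to carers who are "non-responsive to phone calls, emails, texts, or letters and considered lost to follow up". Both conditions are needed, failed contact and a judgement that the carer is lost.
- Consequence: "After withdrawal, no further data will be collected for that participant". This is written once and covers carers who withdraw consent and carers whom staff withdraw.
- Earlier data: "Data that were collected prior to a study participant's withdrawal will be de-identified and still be used in the data analysis for the study".

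Other sections bear on it. At screening (Recruitment Methods item 4, and the screening paragraph of Study Design/Procedures) staff ask whether they may telephone, leave voicemail, text, or "send mail to their mailing address if we are having trouble contacting them by phone or email". Under Research Participant Compensation, "Gift card incentives will be increased over time": $20 at T1, $25 at T2 and $30 at T3. The safety monitoring committee is to watch "differential attrition from the intervention groups" and to look for systematic patterns in missing data. The Data Analysis Plan names a three-group by three-time-point RMANOVA, followed by RMANCOVA if mean differences are found. It states no missing-data method and no analysis set.

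**The concern.** Losing contact with a carer and a carer refusing further data collection are different events. The first may be temporary: T2 and T3 are months apart (6 and 12 months in the Objectives; T3 four to six months after T2 in the instrument table). The second is a decision that the trial must respect. The section gives both the same ending.

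At stake are outcomes from randomised carers who never withdrew consent. Every one not collected reduces information and takes the comparison further from the full randomised group. The loss may also be informative, since the sample is chosen for a recent caregiving transition and the Background describes substantial health decline within six months of one. That is a reasonable worry, not something the documents show.

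The decision also has no written criterion. The consent paragraph of Study Design/Procedures counts interventionists among the research staff, and different interventionists deliver each condition. Nothing in the text keeps knowledge of the arm out of the case review.

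**Working it through.** **1. What the text fixes and leaves open.** It fixes the trigger (no response, and judged lost), the decision-maker (project manager with research staff) and the consequence (collection ends). It leaves open the number of attempts, the period over which they are made, any link to the T2 or T3 window, and whether a carer who resurfaces can return. The form's own instructions for this section ask about partial withdrawal with continued data collection; the plan describes none.

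**2. What is forgone, by time of withdrawal.**

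| Staff withdrawal | Outcomes held | Outcomes forgone | In a complete-case RMANOVA if T3 alone is later obtained? |
|---|---|---|---|
| Before T2 | T1 | T2 and T3 | No, T2 is missing |
| After a missed T2 | T1 | T3 | No, T2 is missing |
| After T2 was obtained | T1, T2 | T3 | Yes |

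The rule can therefore cost T2 as well as T3. A recovered T3 helps a carer without T2 only if the model accepts partial records. For the same reason, keeping earlier data achieves little under complete-case RMANOVA.

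**3. Size.** The target of 350 comes with no alpha, power, effect size or dropout allowance, so there is no plan figure to reproduce. The following is illustration only. Assumptions: equal allocation (350/3 = 116.7 per arm); a fraction L lost at T3; a fraction r of those regained by later attempts; one pairwise T3 comparison with two-sided alpha 0.05 and a standardised difference of 0.4; an analysis that uses every T3 value.

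Expected T3 assessments: N = 350 × (1 − L × (1 − r)). Power: Φ(0.4 × √(m/2) − 1.96), with m = N/3. With no loss, power is 0.86.

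| L | r = 0: N, power | r = 0.25: N, power | r = 0.5: N, power |
|---|---|---|---|
| 10% | 315, 0.83 | 323.8, 0.84 | 332.5, 0.85 |
| 20% | 280, 0.78 | 297.5, 0.80 | 315, 0.83 |
| 30% | 245, 0.72 | 271.3, 0.77 | 297.5, 0.80 |

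Worked cell, L = 20% and r = 0: m = 280/3 = 93.3; 0.4 × √46.7 = 2.73; 2.73 − 1.96 = 0.77; Φ(0.77) = 0.78.

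Assessments regained are 350 × L × r. That is 0 when r = 0, 350 × 0.20 × 0.5 = 35 at 20% loss, and at most 350 × 0.30 × 0.5 = 52.5 in this grid.

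**4. Bias in an arm contrast.** Let f be the fraction missing at T3 in an arm and g the mean of the missing minus the mean of the observed, in SD units. The full mean is the observed mean plus f × g, so the contrast between arms 1 and 0 is off by |f1 × g1 − f0 × g0|. All values below are assumed.

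- Equal loss of 20% with the same gap: 0.
- Loss of 25% against 15%, common gap 0.25 to 0.5: 0.10 × 0.25 = 0.025 to 0.10 × 0.5 = 0.05 SD.
- Loss of 30% against 10%, same gaps: 0.20 × 0.25 = 0.05 to 0.20 × 0.5 = 0.10 SD.
- A gap in one arm only, loss there of 20% to 30%: 0.20 × 0.25 = 0.05 to 0.30 × 0.5 = 0.15 SD.

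Bias therefore requires the loss, or its relation to outcome, to differ by arm. The documents establish neither.

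**The case against.** The best defence is that the rule is narrower than it looks. Withdrawal follows failed contact through several channels and a case review. A reader might infer that an unanswered call, or silence during the 28-day intervention, is enough; the second condition in the sentence rules out the first, and no text links the second to withdrawal. A reader might also infer that such carers are never approached again. The section bars data collection and does not mention contact, although with collection barred a later approach would yield no outcome.

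The defence can add that missed occasions are handled separately elsewhere. The data collection text treats surveys that cannot be obtained as missed, and an HRV reading that cannot be scheduled as missing for that time point, without ending participation. All arms have the same weekly follow-up and gift-card schedule, and the monitoring committee watches attrition by arm. Finally, people who have not answered by phone, email, text or letter may be unreachable under any rule.

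Much of this stands. It removes any claim that the lost outcomes are known to be recoverable, non-random or unequal between arms. It does not remove the rule. The visit-level wording does not override the withdrawal section once a carer is judged lost. Contact channels and incentives work before withdrawal, not after it. Monitoring recovers no data and corrects no estimate.

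**Conclusion.** The point holds as a defect in the follow-up rule. As written, a randomised carer who has not withdrawn consent can be removed by staff on an undefined judgement, and T2 or T3 outcomes obtainable later are then not collected.

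Its size is unknown. The power table rests on assumed loss and recovery rates, including zero recovery, where the gain is nil. At 20% loss it shows power moving from 0.78 to at most 0.83. The stronger conclusion, that the rule biases the comparison of arms, is tempting but unsupported: it needs a difference between arms that the documents do not show. The case for change is that the amendment is cheap, can only reduce missing outcomes, and is not already achieved elsewhere in the protocol.

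**What to change.** Amend Withdrawal of Research Participants so that non-response does not end data collection.

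- Keep every randomised carer who has not withdrawn consent active until the T3 window closes.
- Attempt both T2 and T3 through the existing channels, even if the intervention or an earlier visit was missed. State the number and timing of attempts.
- Assign the lost-to-follow-up label only after the T3 window has closed.
- Record three states separately, by arm: stopped the intervention; missed a visit or lost contact; withdrew consent for data collection. End collection only for the last.
- In the Data Analysis Plan, replace complete-case RMANOVA with an analysis that keeps partial records, such as a likelihood-based mixed model, so that a T3 value counts when T2 is missing. Such a model does not by itself correct for informative loss, which is why the attempts matter as well.

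The cost is a short protocol edit, a change of model and a few extra contact attempts per non-responder. Carers who ask not to be contacted are unaffected.
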